The proposed study tests the novel DilaCheck® device *in vivo*. The target population is women presenting to the hospital for evaluation of labor or admitted to the Labor and Delivery unit for management of the first stage of labor. The Sponsor (Elm Tree Medical Inc.) trains providers working on the Labor and Delivery unit in the use of DilaCheck®. After informed consent, each patient participant is randomized to receive either two cervical dilation examinations with standard methods or two cervical dilation examinations using the device. Two practitioners complete the cervical examinations separately. The primary outcome is inter-examiner agreement between the control and device arms. Secondary outcomes include agreement of subjective measurements with DilaCheck® measurements over time, agreement of providers' device readings with a blinded reviewer's, patient and provider satisfaction, and documentation of adverse events. Planned enrollment is 50 participants over one year. We hypothesize that the device will increase agreement between the two practitioners from about 49% to 90%, as demonstrated in the simulator trial. The long-term objective is to validate DilaCheck® for use in increasing precision in cervical dilation measurements so that this tool may be available to Labor and Delivery providers to enhance quality of care for pregnant mothers. Increased precision in cervical dilation measurements will enable providers

to make better recommendations for admission to the hospital, augmentation or induction of labor, and cesarean section.

The proposed study is a randomized, controlled trial comparing inter-examiner agreement of standard methods for measuring cervical dilation to a novel medical device. The research population is pregnant women in the first stage of labor.

TRIAL PROTOCOL

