Eligibility. Subjects eligible for inclusion in the study must be: pregnant women who are admitted to a Labor and Delivery unit for management or induction of labor in the first stage of labor, are able to give informed consent, are 18 years of age or greater, English-speaking, have intact membranes, and have a gestational age greater than or equal to 37 weeks (i.e. term pregnancy). Inclusion criteria also include having a functioning epidural in place or having provided consent prior to the start of labor. Exclusion criteria include progression to the second stage of labor (i.e. known dilation of ten centimeters), non-English speaking, known prior rupture of membranes, any condition that renders labor unsafe for the patient (e.g. cardiac conditions, pulmonary hypertension) and any other condition that necessitates an emergent or urgent cesarean section (e.g. non-reassuring fetal status, placental abruption, hemorrhage, cord prolapse). Patients are only consented if they have adequate pain control, either because they are not yet in labor (i.e. are admitted for an induction of labor) or have a functioning epidural. All participants are necessarily female due to the subject matter. Given the vulnerability of pregnant patients under the age of 18, this study will exclude children. There are no restrictions on eligibility based on race or ethnicity. Patients can withdraw from participation at any point in the study. DilaCheck® is FDA-cleared for use by qualified healthcare professionals for women in pregnancy and labor without any further restrictions.

Provider Enrollment. The Sponsor, TJU Principle Investigator, or trial coordinator will discuss participation in the trial with providers at the TJU Labor and Delivery unit. Providers will be given the option of participating on a volunteer basis.

Provider Training. The Sponsor will train participating providers in the use of the device. The Sponsor will use a detailed script to ensure standardization of the training. The Sponsor will use a wooden cervical simulator box to train providers to use the study device without patient involvement. The standardized training will test competency with the device using the cervical simulator. The providers will also have access to a training video to reinforce the in-person training.

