Trial Coordination. After training, the Sponsor or the trial coordinator will orient the provider to the study protocol and assign every provider a unique Provider Number. The trial coordinator will arrange with the hospital staff to conduct the trial at scheduled times during the study period. Administration of the trial requires two hospital providers who have been trained to use the device, the trial coordinator,

and a patient.

Patient Enrollment. Hospital providers will screen patients who have been admitted to the Labor and Delivery unit for eligibility. Posters advertising the trial will also be displayed on the Labor and Delivery unit. Once identified, hospital providers will ask eligible patients if they are interested in participating. If a patient indicates interest, the trial coordinator will complete an informed consent. The patient will sign the Patient Informed Consent Form.

Randomization. The trial coordinator will assign the participant a Subject Number from one to 50, in sequential order. (The first patient enrolled is assigned #1, the second enrolled is assigned #2, and so on.) The trial coordinator will then randomize the patient to either the Control Group or the Device Group using a randomization matrix generated by a computer randomization program.

Data Collection. The trial coordinator will inform two trained providers that the patient has agreed to participate in the trial. The trial coordinator will accompany one hospital provider to the patient's hospital room. The second provider will wait outside the room, in a place where s/he cannot hear the interaction in the room. The trial coordinator will re-affirm consent with the patient.

If the patient is randomized to the Control Group: The first provider will introduce him/herself and inform the patient that s/he is going to conduct a cervical examination. The trial coordinator will record the time of the first exam. The provider will complete a cervical examination following the standard techniques s/he uses on a regular basis, using sterile gloves. The provider will dispose of the gloves. The first provider will write his/her measurement of cervical dilation on the first Data Collection Form and fold the sheet of paper. Readings may be integers or fractional answers. The coordinator will take the folded sheet of paper and will not read the value. The first provider will then leave the hospital room. S/he will not speak to the second provider.

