For participants in the DilaCheck® arm, the subjective and DilaCheck®

DilaCheck® Trial

measurements will be plotted along an X-Y axis and the Pearson correlation coefficient between the two data sets will be calculated. This analysis will be completed for both the fractional and integral (non-fractional) sets of DilaCheck® measurement readings.

The photographs of the DilaCheck® measurements will be read by an independent, blinded reviewer to report the DilaCheck® measurements. The provider's and reviewer's DilaCheck® measurements will be plotted along an X-Y axis and the Pearson correlation coefficient between the two data sets will be calculated. This analysis will be completed for the fractional and integral (non-fractional) sets of DilaCheck® measurement readings.

The correlation between the providers' subjective and DilaCheck® measurements will be analyzed over time. To do so, for providers who complete at least 10 exams, the correlation of the two measurements in the provider's first half of examinations will be compared to the providers' second half of measurements. A T-test will be completed to determine whether the two correlations differ significantly. The analysis will be repeated for both the fractional and integral (non-fractional) sets of DilaCheck® measurement readings and using the data sets of readings from the independent reviewer.

The average pain score in each group will be calculated, and a Students T test will be performed to determine whether pain scores differed significantly between groups. Using logistic regression whether provider number, patient age, gestational age, weight, or epidural status significantly impacted likelihood of agreement or pain score within each group will be determined. The average provider confidence in accuracy will be calculated, and a Students T test will compare if patients' confidence differs significantly between groups. Logistic regression will be used to determine if provider experience or training significantly predicted likelihood of agreement.

Any additional statistical analysis appropriate for the data collected will be performed. For the qualitative data, including descriptions of adverse events and feedback, each of the responses will be reviewed individually. Any serious adverse events will be reported. Any informative feedback or themes in the feedback will also be collated.

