Involvement and Characteristics of Human Subjects. The subject population is women presenting to the hospital for evaluation of a diagnosis of labor and women admitted to the hospital Labor and Delivery unit for management of the first stage of labor. Planned enrollment is 50 patients. The subject population is reproductive aged, pregnant women with stable health. In order to be eligible for the trial, a woman must have a term pregnancy (≥ 37 weeks gestation) and be able to complete informed consent. Only patients presenting to or admitted to the Labor and Delivery unit for management of labor are eligible. For instance, a patient presenting to her clinician's office for a routine prenatal appointment is not eligible, or a patient admitted to the Labor and Delivery unit for a scheduled cesarean section who is not in labor is also not eligible. Exclusion criteria include advancement to the second stage of labor, any condition that renders labor unsafe for the patient, and any other condition that necessitates an emergent or urgent cesarean section. This will ensure exclusion of patients with unstable medical situations. This clinical trial necessarily involves the participation of a vulnerable population, pregnant women, because the device is intended for use in pregnant women. All of the conditions outlined in 45 CFR part 46 Subpart B are met.

Sources of Research Material. This trial does not use any biological samples or hazardous materials. The data collected from human subjects includes: records of two cervical dilation measurements, photograph of the device reading, age, race, ethnicity, gestational age, weight, discomfort ratings, epidural status, confidence in accuracy, patient satisfaction, side effects, and comments. The data collected from providers includes: beliefs about agreement of standard cervical dilation measurements, beliefs about agreement of measurements with DilaCheck®, years of experience on Labor and Delivery, role on Labor and Delivery, provider side effects, patient side effects, ease of use of the device, satisfaction with the device, and comments.

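### The within-arm test of epidural status could pick up labor status or dilation instead, because eligibility ties epidural to labor at consent and neither is in the model

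*Combined protocol and SAP*

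**What the plan says.** Four parts of the combined protocol and SAP bear on this.

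- **Entry rule (Trial Protocol, Eligibility).** "Inclusion criteria also include having a functioning epidural in place or having provided consent prior to the start of labor". The same section restricts consent to women with adequate pain control, "either because they are not yet in labor (i.e. are admitted for an induction of labor) or have a functioning epidural".
- **Planned analysis (Statistical Analysis).** Logistic regression is planned on provider number, the woman's age, gestational age and, in the closing words of the sentence, "weight, or epidural status significantly impacted likelihood of agreement or pain score within each group will be determined". Labor status, induction and dilation are not on the predictor list.
- **Data listed (Sources of Research Material).** After the dilation readings, photograph and some demographic items, the list runs "gestational age, weight, discomfort ratings, epidural status, confidence in accuracy, patient satisfaction, side effects, and comments". Labor or induction status appears neither here nor in the Patient Survey section.
- **Population (Protocol Summary).** "The research population is pregnant women in the first stage of labor". Eligibility also asks for the first stage of labor, although it admits women consented before labor begins.

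**The concern.** Under the entry rule, a woman without an epidural at consent is not yet in labor, and a woman already in labor at consent has an epidural. This is a consequence of the design, not a chance imbalance. Randomization does not remove it, because the epidural comparison is made inside each arm.

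The planned epidural term therefore contrasts two groups that may differ in labor status and in dilation as well as in analgesia. Dilation is the quantity being measured and is recorded for every complete pair, but it is not a predictor. If labor or dilation changes how often two examiners agree, that difference could be written up as something the epidural did. For pain, labor and analgesia may pull in opposite directions, so a real benefit of the epidural could be hidden. The word *impacted* invites a causal reading that the comparison cannot carry.

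**Working it through.** **The plan's own figure.** The documents give no power or sample-size figure for this regression. Their only one, five for 80% power, concerns the primary comparison. It reproduces as 5 per group (80.5% by the normal approximation with a difference of 90 − 49 = 41 and SD 23) and has no bearing here.

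**Inputs from the documents.** 25 women per arm; two-sided alpha 0.05; projected agreement 49% (control) and 90% (device).

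**Assumed inputs.** Half the arm in labor; an epidural in 90% of women in labor and 10% of the others (90/10 overlap); no effect of the epidural itself on agreement; agreement lower in labor by 10 to 40 points, centered on 50%. The documents supply none of these.

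**Step 1: expected contrast.** With half the women in labor, P(labor | epidural) = 0.45/(0.45 + 0.05) = 0.9, and P(labor | no epidural) = 0.1. With agreement of 70% before labor and 30% in labor (a 40-point gap):

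- epidural: 0.9 × 30 + 0.1 × 70 = 34%
- no epidural: 0.1 × 30 + 0.9 × 70 = 66%
- odds ratio = (34/66)/(66/34) = 0.27, although the true epidural effect is nil.

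In general, the false difference equals the labor gap × (0.9 − 0.1).

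**Step 2: how often it would be called significant.** Simulated control arms of 25, likelihood-ratio test, epidural as the only predictor, 90/10 overlap:

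| Assumed labor gap in agreement | False epidural difference | Nominally significant |
|---|---|---|
| 0 points | 0 points | about 6% |
| 10 | 8 | about 7% |
| 20 | 16 | about 13% |
| 30 | 24 | about 23% |
| 40 | 32 | about 37% |

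With labor status added to the model at the 40-point gap, the figure returns to about 5%. If labor status is equally common with and without an epidural, the bias is zero whatever the gap.

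**Step 3: pain, as a mean difference.** Bias = labor effect × 0.8. If labor adds 2 points and the epidural removes 2, the crude contrast is −2 + 2 × 0.8 = −0.4 instead of −2. The plan names logistic regression for pain, so this shows the direction of the problem and does not predict the planned output.

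**Step 4: what adjustment can recover.** At 90/10 overlap the correlation of epidural with labor status is 0.8, and the variance inflation is 1/(1 − 0.64) = 2.8. The 25 women then carry the information of about 25 × 0.36 = 9. The chance that the two variables coincide in all 25 women, so that no separate effect can be estimated, is 0.9^25 = 7%. At 95/5 overlap it is 0.95^25 = 28%.

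**The case against.** A reader might infer that epidural status is a complete stand-in for labor and that any epidural finding would be wrong. The documents do not support that, for several reasons.

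- **The tie is fixed at consent, not at examination.** At the examination, "The trial coordinator will re-affirm consent with the patient", so it is a separate step. A woman who consented before labor may be examined in labor, with or without an epidural. If all participants were in the first stage of labor when examined, as the Protocol Summary describes them, labor status would hardly vary and that part of the problem would largely disappear. Dilation would remain unaccounted for.
- **The bias needs a cause.** Nothing in the documents says that labor or dilation alters agreement or pain. For pain, the Discomfort section itself expects a direct benefit from epidurals.
- **The illustration is not the planned model.** It uses epidural alone, without provider number, age, gestational age or weight. A 40-point gap is about as large as the 41-point effect hypothesized for the device, and at 10 points the inflation is slight.
- **The data list may be incomplete.** It omits the exam times that are recorded elsewhere, and the forms are not in the documents.
- **The analysis is secondary and weak in any case.** At 90% agreement the device arm expects 25 × 0.10 = 2.5 disagreements for at least five predictors.

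All of this stands, and it limits the point to what could happen. It would also be wrong to say the trial could not examine agreement by dilation: the readings exist, and the plan leaves room for further suitable analyses. That clause does not settle the matter, because it prespecifies nothing and cannot use a labor-status field that nobody recorded. Uncertainty about labor status at the exam is itself a reason to record it.

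**Conclusion.** The point holds in limited form. As planned, the epidural coefficient cannot be read as an effect of the epidural, because the entry rule links epidural to labor at consent and the model contains neither labor status nor dilation. A labor or dilation effect could be reported as an epidural effect, or could mask one.

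The size is unknown. The 7% to 37% range rests on 90/10 overlap, half the women in labor, gaps of 10 to 40 points, no true epidural effect and epidural tested alone. Looser overlap at the exam, or a smaller gap, brings it toward the nominal 5%. The randomized primary comparison is not affected. The change is worth making because it costs little and determines what this secondary analysis can conclude.

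**What to change.** 1. Add a labor status field (yes/no) at the first exam to the existing form, and cross-tabulate it with epidural status in each arm.
2. In Statistical Analysis, interpret the epidural term only where the two overlap, for example within women in labor or with labor status in the model. Otherwise report it descriptively as an association. Replace *impacted* in either case.
3. Tabulate agreement in each arm by the mean of the pair's two dilation readings, which are already collected.
4. Reconcile the statements that participants are in the first stage of labor with the route that admits women consented before labor.

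The cost is one form field and a few words of analysis text. With 25 women per arm, the separate epidural effect will be imprecise and may not be estimable. If epidural and labor status coincide completely, adding labor status to the model is no remedy and only the descriptive report remains.

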Photograph Review. The Sponsor will train an independent reviewer to read DilaCheck® measurements. The reviewer will be provided the photographs taken of DilaCheck® measurements. The reviewer will report two measurements for each photograph. The first will be his/her reading of the exact DilaCheck® measurement, which may be a fraction. The second reading will be his/her reading of the DilaCheck® measurement rounded to the nearest integer; i.e. the second response can only be an integer, not a fraction.

Continuous Feedback. After any individual provider completes five examinations with DilaCheck®, the provider will be provided feedback about whether his/her DilaCheck® measurement readings match those of the independent reviewer.

Power Calculation. The planned enrollment in the study is 50 patients. The following assumptions were used for the power calculations. The agreement in the Control Group was projected to be 49%,⁴ and the agreement in the Device Group was projected to be 90%, based on the results of the simulator trial. The standard deviation was projected to be 23, also based on the standard deviation in the prior simulator trial. With a two-tailed test with $\alpha=0.05$, a sample size of five yields 80% power. However, a trial with five participants will not yield the desired robustness in evaluation of a novel medical device. Instead, a sample size of 25 subjects in each group is planned to allow for examinations across a wide range of patients and providers. A sample size of 50 yields a power of 100% to detect a difference between the two methods given the above assumptions.

Statistical Analysis. The statistical analysis will use a two-tailed level of significance of 0.05. Using SPSS, the proportion of examinations in each group for which the two providers' examinations differed will be determined. A Students T test will be performed to determine whether this difference is significant. The number of examinations for which providers' answers differed by one centimeter and by two or more centimeters for each group will be determined. A Students T test will be performed to determine if the frequency of variation of one centimeter significantly differed between groups. A Students T test will be performed to determine if the frequency of variation of two or more centimeters significantly differed between groups. These analyses will be completed for both the fractional and integral (non-fractional) sets of DilaCheck® measurement readings.

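### The agreement regressions use single-provider predictors for an outcome produced by two examiners, and the plan states neither the unit of analysis nor how two providers' values enter

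*Combined protocol and SAP*

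**What the plan says.** The Protocol Summary sets the design for each patient: "Two practitioners complete the cervical examinations separately". The Statistical Analysis section measures disagreement as "the proportion of examinations in each group for which the two" providers' readings were not the same. Its missing-data paragraph drops a patient from the primary outcome if either reading is absent. Agreement therefore exists once per patient and needs both examiners.

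Provider variables are recorded one provider at a time. Trial Coordination gives each provider a number, and the Provider Survey collects each provider's years of experience and role.

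The Statistical Analysis section then plans two logistic models of agreement. The first, fitted within each group, is described as "Using logistic regression whether provider number, patient age, gestational age, weight, or epidural status significantly impacted likelihood of agreement" (or pain score). The second reads "Logistic regression will be used to determine if provider experience or training significantly predicted likelihood of agreement". The test level is given once: "The statistical analysis will use a two-tailed level of significance of 0.05". For neither model does the section say what one row of data is, how two providers' values are combined for one outcome, or whether repeated outcomes are adjusted for. The general allowance for further suitable analyses does not define these models.

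**The concern.** Read literally, a model with one provider number or one experience value per row leaves two options: write each patient's outcome on two rows, one per examiner, or leave one examiner out. The plan chooses neither, so the choice would fall to whoever builds the file after the data are in.

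The two-row layout is easy to slip into, because the data arrive on one form per examination. It makes 25 outcomes look like 50. Patient-level covariates in the same model would then look more precisely estimated than they are. Leaving one examiner out makes the result depend on an arbitrary selection.

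The experience question also carries weight. The Protocol Summary reports that in the simulator the device was equally accurate whatever the user's experience or training level, so readers are likely to take the second model as the clinical check of that statement.

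**Working it through.** **1. The plan's own figures.** The Power Calculation inputs are "The agreement in the Control Group was projected to be 49" per cent, "the agreement in the Device Group was projected to be 90%, based on the results of the simulator trial" and "The standard deviation was projected to be 23, also based on the standard deviation in the prior simulator trial", with two-sided alpha 0.05.
- n per group = 2 × 23² × (1.96 + 0.84)² / 41² = 4.94, rounded up to 5 (power 0.805). The stated five reproduces if read as per group.
- At 25 per group: 41 / (23 × √(2/25)) = 6.30, and 6.30 − 1.96 = 4.34, so power is above 0.9999. The stated 100% reproduces.

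These figures concern the primary comparison. The plan gives no figure for the regressions.

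**2. Outcomes and rows.** There are 25 agreement outcomes per arm. One row per examination gives 25 × 2 = 50 rows per arm and 100 overall, from 50 outcomes. At the assumed rates the expected disagreements are 25 × 0.51 = 12.75 (control) and 25 × 0.10 = 2.5 (device). A stacked file would show 25.5 and 5.

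**3. Effect on a test.** Take one predictor x with no true effect, variance s², and correlation r between its two values in a pair. The two rows of a pair share the same outcome, so each pair contributes (y − p)(x₁ + x₂) to the score, with x centred. Its variance is p(1 − p) × 2s²(1 + r). Ordinary logistic regression assumes independent rows and uses p(1 − p) × 2s². The ratio is 1 + r, so

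true alpha = 2 × [1 − Φ(1.96 / √(1 + r))].

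A patient-level covariate is the same on both rows, so r = 1: the standard error is too small by √2 = 1.41, and alpha = 2 × [1 − Φ(1.386)] = 0.166. For provider variables r is not given in the documents, so the range below is assumed.

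**4. Simulation check.** Likelihood-ratio test, up to 4,000 null data sets per setting (about 3,600 usable at 90% agreement). The 69.5% is the average of 49% and 90%.

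| r | 1 + r | Formula | 25 pairs, 49% | 25 pairs, 90% | 50 pairs, 69.5% |
|---|---|---|---|---|---|
| 1 (patient covariate, or identical providers) | 2 | 0.166 | 0.185 | 0.187 | 0.174 |
| 0.5 | 1.5 | 0.110 | 0.124 | 0.107 | 0.121 |
| 0 (unrelated) | 1 | 0.050 | 0.056 | 0.052 | 0.049 |
| −0.5 (e.g. senior paired with junior) | 0.5 | 0.006 | 0.008 | 0.006 | 0.006 |

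With one row per pair and the pair mean as predictor, the simulated rate was 0.05 to 0.07 in every setting.

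If provider number is entered as indicators, each indicator can equal 1 on at most one of a pair's two rows, because the two examiners differ. Its r is then negative, and stacking makes that test conservative.

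**The case against.** The strongest reply is that nothing in the plan says the file will be stacked. That stands: the 17% is conditional. What is certain is that the row and the coding are unstated. Nor does a rate of 17% per null covariate mean that false predictors will necessarily be reported.

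Four stronger readings are tempting, and the documents do not support them.
- *That the models cannot be fitted at patient level.* They can. Examination order is recorded, so first- and second-examiner columns, or the pair's mean and difference, would hold both providers.
- *That the experience or training test has three times its nominal error.* That sentence names no patient-level covariate. For provider variables the error ranges from below 5% to 17%, depending on an unknown correlation.
- *That using one examiner per pair halves the information.* The number of outcomes stays at 25 per arm, and no such loss has been shown.
- *That the primary test is inflated because its proportion is worded in terms of examinations.* The sentence goes on to refer to both providers' findings, the Power Calculation counts 25 subjects per group, and the missing-data rule removes whole patients. The unit of the primary test is the patient, and the wording is merely loose.

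It is also fair to say that these are supporting analyses, and that with about 2.5 expected disagreements the device-arm model will say little whatever the unit. That limits what the correction can gain, but it does not justify leaving the model undefined.

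**Conclusion.** The concern holds as a mis-stated model in secondary analyses. The outcome is defined per patient, three of the named predictors are defined per provider, and nothing in the plan reconciles the two.

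If the models are run by examination without adjustment, inflation to about 17% (formula 16.6%, simulated 17% to 19%) is established only for age, gestational age, weight and epidural status in the first model. For provider variables the size and direction are unknown.

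These figures assume one predictor at a time, a large-sample formula, and patients independent of each other. Providers who recur across patients are a separate matter. The same coding question applies to pain if the survey gives one score per patient, which is an assumption because the form is not shown.

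**What to change.** - State that every agreement model has one row per patient.
- Replace provider number, experience and training with a small set of pair-level terms fixed before the data are seen: for example the mean and difference (or the minimum) of the two examiners' years of experience, and whether their roles match.
- For clarity only, reword the primary proportion in terms of patients (examiner pairs). The test, sample size and power stay as they are.
- Optionally, add an examination-level analysis of provider-minus-reviewer device readings. Fit provider as a random effect: experience is a single value per provider, so fixed provider effects would absorb it. Label it a supplementary analysis of reading accuracy. It covers the Device Group only, because only that group has device readings and photographs, and it does not replace the agreement analysis.

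No new data are needed. The cost is a few sentences, slightly more programming, and less favourable p-values than a stacked file would show for the patient-level covariates.
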